Primary objective: To conduct an RCT that examines the efficacy of e-Motivate versus a control condition for increasing screening colonoscopy uptake in Black/African Americans. Black/African American patients referred for a screening colonoscopy will be recruited to the RCT. Participants (N=200) will be randomly assigned to an e-Motivate group (N=100) or a control group (N=100). Participants in e-Motivate group will receive usual care and will also complete a one-time, 20-minute e-Motivate app on a tablet immediately following the primary care appointment in which they received a referral for a screening colonoscopy. Participants in the control group will receive usual care (e.g., print handout, patient navigation). It is hypothesized that participants in e-Motivate condition will be more likely to complete the recommended screening colonoscopy.

 Mount Sinai	Protocol Name:	Internet-based Motivational Interviewing for Colonoscopy in African Americans
	Principal Investigator:	[name]
	Primary Contact Name/Contact Info:	[name], [contact] ,
	Date Revised:	8/16/19
	Study Number:	GCO# 14-0275 IF# HS#

Exploratory Aim 2a. To explore the efficacy of e-Motivate for improving a secondary adherence outcome (e.g., bowel prep quality).

Exploratory Aim 2b. To explore mediators and moderators of e-Motivate. As a part of the RCT, potential mediators (i.e., competence, autonomy, relatedness) and moderators (i.e., demographics, Internet fluency/use) will be explored.

2) Background

Colorectal cancer (CRC), a largely preventable disease, remains the second cause of cancer death in the United States in men and women combined. Compared to other racial groups, Black/African Americans have the highest CRC morbidity and mortality rates. Given these disparities, it is critical to increase Black/African Americans' participation in CRC prevention efforts.

A motivational interviewing (MI) intervention can help improve Black/African Americans' screening colonoscopy uptake. MI is a brief patient-centered intervention that increases perceived competence, autonomy, and relatedness in order to promote behavioral change. Extensive research supports the efficacy of MI to promote preventive health screening uptake (e.g., increase HIV testing) and MI has proven efficacious with Black/African Americans across a wide range of diseases. There is strong support for the use of MI to improve Black/African Americans' screening colonoscopy uptake.

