If the patient is interested in participating in the study, but unable to complete the study after the clinic visit (e.g., time constraints, first contact with patient navigator is over the telephone, RA is not on site), the patient can provide the healthcare professional (physician or patient navigator) with permission to be contacted by the study research team. The healthcare provider (e.g., patient navigator or physician) will then give the research staff the patient's preferred contact information. The research staff members will then contact the patient to arrange for a convenient time to meet to complete the consent and intervention.

b) Inclusion and Exclusion Criteria

Eligibility criteria include: 1) self-identify as Black/African American; 2) received a referral for a screening colonoscopy; and 3) English speaking

Healthcare providers (e.g., primary care physicians and gastroenterologists) will determine whether the patient is medically eligible for a screening colonoscopy (e.g., age eligible for a screening colonoscopy based on published guidelines).

Exclusion include: 1) hearing or vision impaired; 2) Phase I participant

c) Number of Subjects

200 participants (100 per condition)

d) Study Timelines

The total study duration is 5 years (September 2015-October 2020).

Years 1-2: Create and field test e-Motivate

Years 3-4: Enroll participants in RCT (Phase II)

 Mount Sinai	Protocol Name:	Internet-based Motivational Interviewing for Colonoscopy in African Americans
	Principal Investigator:	[name]
	Primary Contact Name/Contact Info:	[name], [contact] ,
	Date Revised:	8/16/19
	Study Number:	GCO# 14-0275 IF# HS#

Years 4-5: Conduct follow up medical chart reviews. Conduct qualitative follow up interviews. Conduct all data analyses.

e) Endpoints

Participants in the RCT will have their medical charts reviewed, six months following the initial referral, to determine if the colonoscopy has been completed. Secondary outcomes (e.g., bowel prep quality, number of cancellations) will also be recorded. Participants will also complete a demographics assessment and a questionnaire that assesses mediators (autonomy, competence, relatedness).

There are no events/results that would cause a study subject's participation to end due to safety.

f) Procedures Involved in the Human Research

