The e-Motivate app will be administered on a touchscreen tablet, which the RA will provide to the participant. Depending on the participants responses to prompts in the app, the app could take up to 20 minutes to complete.

Description of the Intervention:

Demonstration video: brief video explaining to the users how to use the app (e.g., “press next to go to the next page”)

Introduction video: brief video welcoming participants to the app and providing a brief overview of the app

Education: True/False questions about CRC prevention (e.g., “colorectal cancer is one of the leading causes of cancer death in the US). Optional educational text and videos (adapted from mentors’ previous work).

Motivational Interviewing Exercises: Decisional balance (pros/cons), reviewing previous success video, looking forward/looking backward, reviewing social support, reviewing personal strengths. All of the motivational interviewing exercises are designed to resolve ambivalence, improve participants’ self-efficacy of having a screening colonoscopy, and motivate participants to get screened.

Action Plan Video: Participants will view a brief video that will review the steps they need to take in order to complete the colonoscopy (e.g., 1. Schedule procedure, 2. Follow doctor’s instructions for completing the prep. 3. Identify someone to take them home after the procedure).

RCT Procedures:

200 participants will be enrolled in an RCT that examines the efficacy of e-Motivate for improving screening colonoscopy uptake among Black/African American patients. A HIPAA waiver was requested in order for the study team to review the information provided on CERNER and EMR to assess for eligibility. In particular, at the beginning of

 Mount Sinai	Protocol Name:	Internet-based Motivational Interviewing for Colonoscopy in African Americans
	Principal Investigator:	[name]
	Primary Contact Name/Contact Info:	[name], [contact] ,
	Date Revised:	8/16/19
	Study Number:	GCO# 14-0275 IF# HS#

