each recruitment day, the RAs will use the CERNER list and EMR to review patients' race, age, and previous colonoscopy history. RAs will alert healthcare providers (e.g., physicians and patient navigators) daily of patients who may be eligible for a screening colonoscopy referral. If a patient is eligible for the study (e.g., self-identifies as black/African American, age-eligible for CRC screening, and received a referral for a screening colonoscopy), the physician or patient navigator will briefly introduce the study to the patients at the end of the primary care or GI appointment. Patients who are interested in participating in the study will meet with an RA in a private exam room immediately following their appointment to review and complete the consent form.

If the patient is interested in participating in the study, but unable to complete the study after the clinic visit (e.g., time constraints, first contact with patient navigator is over the telephone, RA is not on site), the patient can provide the healthcare professional (physician or patient navigator) with permission to be contacted by the study research team. The healthcare provider (patient navigator or physician) will then give the research staff the patient's preferred contact information. The research coordinator will then contact the potential participant and schedule a date/time to complete the consent form.

Consented participants will complete a verbally administered baseline questionnaire. Participants will then be assigned to one of two groups: e-Motivate (N=100) or control group (N=100). Participants assigned to e-Motivate condition will receive usual care and will also complete the 20 minute e-Motivate app. Immediately after completing the e-Motivate app, the RA will verbally administer a post-intervention questionnaire that assesses the hypothesized mediators. Participants in the control group will receive usual care (e.g., patient navigation, print materials). Participants will receive \$20 gift card to Target as compensation. Six months following the initial referral, medical charts will be reviewed to determine whether the colonoscopy was completed, the quality of the bowel prep, and process variables (e.g., number of cancellations/rescheduled appointments/no-shows)

g) Specimen Banking

N/A

h) Data Management and Confidentiality

Survey Data:

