Throughout the study, quantitative survey data will be collected. The survey data will be scanned and uploaded on our Department's secure internet server (J drive). The hard copies of the surveys will be stored in a locked filing cabinet in the CAM building. Each participant's data will be de-identified and assigned an anonymous ID number. A "cross-over" file matching ID number with participant identifying information (name, address and phone number) will be maintained and stored separately on our department's secured and encrypted intranet server. Only study personnel will have access to the crossover file.

 Mount Sinai	Protocol Name:	Internet-based Motivational Interviewing for Colonoscopy in African Americans
	Principal Investigator:	[name]
	Primary Contact Name/Contact Info:	[name], [contact] ,
	Date Revised:	8/16/19
	Study Number:	GCO# 14-0275 IF# HS#

CERNER Data:

In addition, as part of the RCT, we will first obtain the CERNER list to identify the Black/African American patients who are age eligible or CRC screening and are scheduled for a primary care or GI appointment that day. We will then access EMR to identify whether the patient may be eligible for a screening colonoscopy (has not had a recent screening colonoscopy procedure in the EMR). We have requested a HIPAA waiver. We will then alert the physicians and patient navigators of the patients who may be eligible or our study. The CERNER list will be destroyed at the end of each recruitment shift.

App Engagement Data:

We will record participants' engagement with e-Motivate. The e-Motivate will be linked to an electronic database that will be entirely anonymous and will only record the participants' overall engagement (e.g. responses to the exercises, amount of time spent on each exercise, etc.). The database will initially be stored on the AppLab's encrypted server. The anonymous dataset will then be sent to the Mount Sinai investigative team.

Outcome Data:

Six months following the initial visit, we will check the medical records of all consented participants in Phase II to obtain outcome data (e.g., colonoscopy completion status, prep quality, # of cancellations/rescheduled appointments/no-shows, receipt of PN/care coordination). The medical information will be de-identified and stored on a password protected file on Mount Sinai's intranet server.

DATA ANALYSES

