Missing data: The e-Motivate is a one-time intervention and thus we anticipate minimal missing data. *Analyses of covariates:* Participants will be randomly assigned to treatment condition and therefore significant baseline differences are not expected. However, contingency tables and t-tests will be performed to determine any differences between the two groups. Using a p value of ≤ 0.15 , any consistent pattern of correlation for any of the covariates would suggest their inclusion in the primary data analysis model.

Analysis of Primary Outcome: The primary outcome (screening uptake) will be assessed with a logistic regression model. The hypothesized moderators will be evaluated individually. The final logistic model will contain the main effect for the treatment group, any identified covariates, and any significant moderators.

Analysis of Secondary Outcome: If bowel prep quality is normally distributed, a t-test will be used to compare the two treatment groups.

Exploration of Mediation: In the mediation analyses, we will first show that treatment predicts the primary outcome. We will next evaluate the extent to which the treatment affects the mediators using a linear mixed model with repeated measures. Time will be entered into the model first followed by any covariates. Next, the binary treatment vector will be introduced as a main effect followed by interaction with time. Since there are three

 Mount Sinai	Protocol Name:	Internet-based Motivational Interviewing for Colonoscopy in African Americans
	Principal Investigator:	[name]
	Primary Contact Name/Contact Info:	[name], [contact] ,
	Date Revised:	8/16/19
	Study Number:	GCO# 14-0275 IF# HS#

correlated mediators, the p-values will be adjusted using the Sidak correction for multiple comparisons. Only the mediators that are predicted by the treatment main effect or the time by treatment interaction will be retained. Each mediator will then be introduced into the logistic model predicting the primary outcome. To establish mediation, the indirect paths from treatment to mediators and from mediators to outcomes will be assessed using 1000 bootstrap samples following the procedures.

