Analysis of Power: We are proposing a sample of 200 participants (100 in each treatment arm) and setting alpha equal to 0.05. In our pilot study, the MI condition was associated with 71.4% (20/28) screening uptake compared to 52.0% (13/25) for the control condition. Based on these results, we are hypothesizing that approximately 71.4% of participants in e-Motivate condition will complete the colonoscopy, compared to approximately 52% of the participants in the control condition. Based on these projections, power is equal to 0.83. Of note, for the proposed study, the control condition will be a print brochure. Previous research suggests that a print brochure produces comparable CRC screening rates (52.0%-53.5%) to our pilot study's attention control condition (52.0%).

i) Provisions to Monitor the Data to Ensure the Safety of Subjects

Part I: Elements of a Data and Safety Monitoring Plan

1. List the name(s) of the individual(s) at the Mount Sinai School of Medicine (MSSM) who will be responsible for data and safety monitoring of this study. For each individual, indicate their role, name, title, and department information.

MSSM Principal Monitor:

Check One: PI: Team Member: Independent:

Last Name: [name]

First Name: [name]

Academic Title: Instructor

Department: Oncological Sciences

Mailing Address: [name]

[contact]

[contact]

E-mail: [contact]

MSSM Additional Monitor:

Check One: PI: Team Member: Independent:

Last Name: [name]

First Name: [name]

Academic Title: Professor

Department: Oncological Sciences

Mailing Address: [name]

[contact]

 Mount Sinai	Protocol Name:	Internet-based Motivational Interviewing for Colonoscopy in African Americans
	Principal Investigator:	[name]
	Primary Contact Name/Contact Info:	[name], [contact] ,
	Date Revised:	8/16/19
	Study Number:	GCO# 14-0275 IF# HS#

[contact]
E-mail: [contact]

2. Justify your choice of principal monitor in terms of the assessed risk to the research subject's health and wellbeing. In high risk studies when the principal monitor is independent of the study staff, indicate the individual's credentials, relationship to the PI, and the rationale for selection.

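### The bowel prep t-test can use only participants who had a procedure, so it loses the protection of randomisation to the extent that the app changes who has one

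*Combined protocol and SAP*

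**What the plan says.** Section 1 (Objectives) gives Exploratory Aim 2a as "To explore the efficacy of e-Motivate for improving a secondary adherence outcome (e.g., bowel prep quality"). The rating comes from chart review six months after referral: under RCT Procedures in section 5f, "medical charts will be reviewed to determine whether the colonoscopy was completed, the quality of the bowel prep, and process variables" are collected together. The Outcome Data paragraph of section 5h says "we will check the medical records of all consented participants in Phase II to obtain outcome data".

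The analysis is one sentence, under Analysis of Secondary Outcome in section 5h: "If bowel prep quality is normally distributed, a t-test will be used to compare the two treatment groups". It names no analysis set and does not say what happens to participants who never have a procedure. The missing-data statement in the same section expects little missing data because the intervention is given once. That reason does not cover an outcome read from the chart months later.

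Analysis of Power projects that "approximately 71.4% of participants in e-Motivate condition will complete the colonoscopy, compared to approximately 52% of the participants in the control condition", and the primary hypothesis is that the app raises completion.

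Section 5e adds that "Secondary outcomes (e.g., bowel prep quality, number of cancellations) will also be recorded". Cancellations, reschedulings and no-shows do not require a completed procedure, so this point concerns the prep test only.

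**The concern.** The documents do not say outright that only people who had a procedure can be rated, but it follows from what a prep rating is. Having a rating is therefore an event after randomisation, and one that the app is meant to change. If the app succeeds on the primary outcome, its rated group will include people who would not have attended under usual care. Those people may prepare better or worse than the rest.

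The Action Plan Video makes the two effects hard to separate: "Participants will view a brief video that will review the steps they need to take in order to complete the colonoscopy", and those steps include both scheduling and following the prep instructions. A real effect on prep is plausible, but the planned test cannot tell it from a change in who attends. At stake is how a secondary result is read. A real prep benefit could be hidden or reversed, or a difference in who attended could be reported as efficacy on prep.

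**Working it through.** **Inputs from the documents.** 100 per arm, alpha 0.05, projected completion 71.4% (20/28 in the pilot) and 52.0% (13/25), all from Analysis of Power. Two-sided testing is assumed, because sidedness is not stated.

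**The plan's own figure.** Power for 71.4% vs 52% with 100 per arm is 0.810 (pooled variance) or 0.821 (unpooled). The plan states 0.83, which is close enough. The completion rates are all that is needed below.

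**Share without a rating.** 1 − 0.714 = 28.6% vs 1 − 0.52 = 48.0%, a gap of 19.4 points. About 71 vs 52 people would enter the test. These shares are upper limits, since an abandoned procedure may still be rated. If 5% of attempts were abandoned but rated (assumed), the rated shares are 0.714/0.95 = 75.2% and 0.52/0.95 = 54.7%, leaving about 25% vs 45% unrated. At 10% (assumed), about 21% vs 42% are unrated.

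**Bias with no app effect on prep.** Assume that a latent tendency to attend has correlation ρ with a normally distributed prep score. The documents give neither ρ nor its sign. Among those rated, the mean of the latent tendency is φ(z_p)/p:

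- app: 0.3401/0.714 = 0.476
- control: 0.3984/0.52 = 0.766
- difference: −0.290, so the bias is −0.290ρ SD

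With standard errors of 0.1802, 0.1776 and 0.1688 for 71.4 vs 52 rated, the normal approximation gives the following for positive ρ:

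| ρ | Bias (SD) | False result favouring app: 1 − Φ(1.96 + abs(bias)/SE) | False result against app: 1 − Φ(1.96 − abs(bias)/SE) | Total |
|---|---|---|---|---|
| 0.2 | −0.058 | 1.1% | 5.1% | 6.2% |
| 0.3 | −0.087 | 0.7% | 7.1% | 7.8% |
| 0.5 | −0.145 | 0.2% | 13.5% | 13.8% |

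Simulating the pooled t-test gave totals of 6.2%, 7.8% and 13.5%. For negative ρ, the sign of the bias and the two middle columns swap.

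**Sensitivity of these figures.**

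- Equal attendance in the two arms: the two means are equal, so the bias is zero at every ρ and the test keeps its 5%.
- Completion of 62% vs 52% (assumed): the difference in means is 0.614 − 0.766 = −0.152. The bias is 0.03, 0.05 or 0.08 SD in size, and total rejection is about 5%, 6% or 7%.
- 10% of attempts abandoned but rated: bias 0.06, 0.10 or 0.16 SD in size, total rejection about 7%, 9% or 16%.

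**Trimming bounds.** If the app deters no one, the share of rated app participants who attended only because of the app is q = 1 − 0.52/0.714 = 0.272. Removing that share from the top or the bottom of a normal score moves the app mean by φ(z_q)/(1 − q) = 0.3317/0.728 = 0.455 SD. At 62% vs 52%, q = 0.161 and the shift is 0.292 SD.

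**What the bounds would do to a result.** The just-significant difference with 71.4 vs 52 rated is 1.980 × √(1/71.4 + 1/52) = 0.361 SD. Its lower bound is 0.361 − 0.455 = −0.094, so zero is not excluded. The difference detectable with 80% power, about 0.51 SD, gives 0.51 − 0.455 = 0.055, which excludes zero as a point estimate. Sampling error is not included in these bounds.

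**The case against.** The strongest case against has four parts.

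- **The imbalance is only a projection.** It comes from a pilot of 28 vs 25 people. This stands: if the app does not change who has a procedure, there is no selection bias. A reader might infer that the test is certain to be biased or simply non-randomised. The documents support only the conditional statement.
- **The consequence is not automatically a false claim for the app.** A reader might take the inflated rejection rates as a raised risk of false efficacy. The rates are two-sided totals. Under positive correlation, false results favouring the app fall below the nominal 2.5%, and the excess lies on the other side. Only a negative correlation raises the risk of false efficacy, and no document gives the sign. This stands in full.
- **The size is assumed and mostly small.** At correlations of 0.2 to 0.3 the bias is 0.06 to 0.09 SD, well under the 0.36 SD needed for significance. This stands too. The bias matters only if both the attendance effect and the correlation are large.
- **The aim is already exploratory, and prep quality is naturally understood among people who had a procedure.** This stands in part. No further exploratory label is needed. But the word exploratory warns of weak evidence. It does not tell a reader that the groups compared may no longer be the randomised ones, and nothing else in the plan says so.

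**Conclusion.** The structural point holds, conditionally. The prep comparison is among participants with a rated procedure, and it is unprotected by randomisation to the extent that the app changes who has one. At the projected rates up to 28.6% vs 48.0% would be unrated.

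Confidence is high for that structure but not for the size or direction of bias, which the documents cannot settle. The figure of about 0.06 to 0.15 SD rests on an assumed normal score and an assumed correlation of 0.2 to 0.5 in absolute value. It shrinks to about 0.03 to 0.08 SD at 62% vs 52%, and to zero with equal attendance.

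A reader might extend the concern to the trial's main conclusion. The documents do not support that: completion is sought in the charts of all consented participants, and neither the primary analysis nor the sample size depends on the prep rating. This is a low-cost improvement to one exploratory result.

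**What to change.** In Analysis of Secondary Outcome, section 5h:

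1. State that prep quality is compared among participants with a rated procedure, and report the number rated in each arm.
2. Describe the result as conditional on having a procedure and not protected by randomisation.
3. Report trimming (selection) bounds beside it as a sensitivity analysis. State that they assume the app deters no one, and that they apply only to people who would have a procedure under either arm.

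As a minor side note, the sentence could also name a rank or ordinal method for a rating that is categorical or not normal. That deals with the distribution only and does not replace items 2 and 3.

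An all-randomised summary of colonoscopy completed with adequate prep is not recommended as a substitute. It would be driven largely by attendance, so it would mostly restate the primary outcome.

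The cost is a few sentences and a short extra analysis of chart data already being collected. The downsides are a weaker claim about prep quality and bounds that may be too wide to settle the question: about ±0.46 SD at the projected rates for an assumed normal score, so a just-significant difference would not exclude zero.

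### The mediation plan for exploratory Aim 2b opens with a total-effect step its bootstrap does not need, and its Sidak correction cites three mediators although each can be retained on either of two tests

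*Combined protocol and SAP*

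**What the plan says.** Section 1) Objectives lists the mediators of Aim 2b, namely competence, autonomy and relatedness, and labels the aim exploratory. The analysis is in section 5) Study Design, h), under DATA ANALYSES, Exploration of Mediation. It runs in this order:

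1. "In the mediation analyses, we will first show that treatment predicts the primary outcome".
2. A repeated-measures linear mixed model for the mediators, with time, covariates, treatment and then treatment by time. Because there are three correlated mediators, "the p-values will be adjusted using the Sidak correction for multiple comparisons".
3. "Only the mediators that are predicted by the treatment main effect or the time by treatment interaction will be retained".
4. Each retained mediator enters the logistic model for uptake, and the indirect paths are assessed with 1000 bootstrap samples.

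The text does not say what happens if step 1 fails, and does not write out the number of tests in the Sidak family.

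Section 5) f), RCT Procedures, describes a baseline questionnaire for all participants. It describes a post-intervention mediator questionnaire only for those who have just finished the app.

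**The concern.** There are two separate points.

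**The first step.** The bootstrap in step 4 tests the indirect effect directly, so a demonstrated total effect is not a requirement for it. Used as a condition, step 1 can only remove analyses. It removes them when uptake shows no significant difference, which is when the trial team would most want to know whether the app moved competence, autonomy or relatedness.

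**The correction.** The reason given for Sidak is the count of mediators. The retention rule accepts either of two effects for each mediator, so the screen contains 2 × 3 = 6 tests. A correction sized for three would leave its error above the intended 5%.

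At stake are some of the information available for Aim 2b and the meaning of the adjusted p-values in the screen. The primary analysis is not affected.

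**Working it through.** **Inputs.** From Analysis of Power: 100 per arm, "setting alpha equal to 0.05", and pilot rates given as "the MI condition was associated with 71.4% (20/28) screening uptake compared to 52.0% (13/25) for the control condition". Sidedness is not stated; two-sided is assumed. The documents give neither the correlation among mediators nor any effect size on or from a mediator, so those values below are assumptions.

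**1. The plan's own figure.** The plan says: "Based on these projections, power is equal to 0.83". With pooled variance under the null:

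- mean rate = (0.714 + 0.52)/2 = 0.617
- SE under the null = √(2 × 0.617 × 0.383/100) = 0.0687
- SE under the alternative = √((0.714 × 0.286 + 0.52 × 0.48)/100) = 0.0674
- power = Φ((0.194 − 1.96 × 0.0687)/0.0674) = Φ(0.88) = 0.81

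Other methods give 0.821 (unpooled), 0.812 (arcsine) and 0.799 (Wald on the log-odds). The stated 0.83 is reproduced to within about 2 points.

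**2. Chance that step 1 fails.** At the design effect this is 1 − 0.83 = 17% on the stated power and 1 − 0.81 = 19% recomputed. With control uptake at 52% and smaller differences (assumed), the pooled formula gives:

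| True difference (points) | Power | Step 1 fails |
|---|---|---|
| 19.4 (design) | 0.81 | 19% |
| 18 | 0.75 | 25% |
| 15 | 0.58 | 42% |
| 12 | 0.40 | 60% |
| 10 | 0.30 | 70% |

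**3. Cost in detecting a real indirect effect.** This was simulated with 100 per arm, post-scores in both arms, an app effect of 0.5 SD on the mediator, a mediator effect of 0.5 log-odds per SD on uptake, and uptake of 71.4% v 52%. Mediation counted as found when both paths were significant, with the treatment-to-mediator path at the Sidak level; this stands in for the bootstrap. The chance of finding it is about 0.79 without step 1 and 0.65 with it. As a rough check, 0.79 × 0.81 = 0.64.

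**4. Error of the screen.**

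- Sidak level for three tests: 1 − 0.95^(1/3) = 0.01695
- That level applied to six independent tests: 1 − (1 − 0.01695)^6 = 9.75%
- Sidak level for six tests: 1 − 0.95^(1/6) = 0.0085

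For correlated mediators, 1,000,000 draws of the six test statistics were simulated. The main effect (mean over both times) and the interaction (change) were taken as independent, which holds when variances are equal at the two times.

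| Mediator correlation | Six tests at 0.01695 | Six tests at 0.0085 | One test per mediator at 0.01695 |
|---|---|---|---|
| 0 | 9.7% | 5.0% | 5.0% |
| 0.5 | 8.8% | 4.6% | 4.5% |
| 0.7 | 7.8% | 4.1% | 4.0% |
| 0.8 | 7.1% | 3.7% | 3.6% |
| 0.95 | 5.2% | 2.7% | 2.6% |

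If the main effect is coded at baseline instead, the six-test error at 0.01695 is 6.5% to 9.4% for mediator correlations of 0.8 to 0 and pre-post correlations of 0.3 to 0.7.

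**The case against.** Requiring a total effect first is a recognised causal-steps convention and a conservative choice for an exploratory aim. The sentence may also state only an order of work, since no stop rule is written. The adjustment could be meant to cover both model terms, since the number of tests is not stated. These points stand: the gate and the three-test count are the natural readings, but both are inferred.

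Three stronger readings are tempting and are not supported.

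- **That the plan often blocks Aim 2b.** On its own figures the block is about one trial in six to one in five. Rates of 42% to 70% need true differences of 15 to 10 points, which the documents do not give.
- **That detection of mediation collapses.** At an assumed 62% v 52%, the same simulation falls from 0.80 to 0.27. But it holds the indirect effect at 0.5 × 0.5 = 0.25 log-odds while the total effect falls from 0.83 to 0.41 log-odds. The mediated share thus rises from 30% to 61%. If the indirect effect weakened with the total effect, detection without step 1 would fall too.
- **That false mediation claims nearly double.** A wrongly retained mediator must still pass the bootstrap. The full sequence was simulated with no app effect on any mediator (mediator correlation 0.5, pre-post correlation 0.5 to 0.7, post-scores in both arms, a Monte Carlo interval for the product standing in for the bootstrap). The screen passed something in 8% to 10% of runs, but a false claim followed in only 0.1% to 4.6% without step 1 and 0% to 2.8% with it.

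**Conclusion.** The point holds as a minor improvement to an exploratory analysis.

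The total-effect step is unnecessary given the bootstrap. Read as a gate, it costs Aim 2b about 17% to 19% of trials at the design effect. It also costs about 14 percentage points (0.79 − 0.65) in the chance of finding a real indirect effect, under assumed effects that the documents do not supply.

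If Sidak counts three tests, the screen runs at about 7% to 9% for mediator correlations of 0.8 to 0.5. The 9.75% figure is the limit for independent mediators, and the plan itself calls them correlated. The excess belongs to the screen alone.

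One matter comes before both. The plan's time-by-treatment term needs mediator scores at two times in both arms, and the procedures describe the second only after the app. If controls have none, that term cannot be estimated.

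**What to change.** 1. Reconcile section 5) f) with the mediation model: state whether control participants complete the second mediator questionnaire, and when. The plan's model and the changes below both depend on it.
2. Remove the total-effect step as a condition. Bootstrap the indirect effect for all three mediators whatever the primary p-value, labelled exploratory, with Sidak-adjusted intervals for three tests (1 − 0.01695 = 98.3%).
3. If the screen is kept, pre-specify one test per mediator, either time by treatment or the post-score adjusted for baseline, so that the three-test level is right. Otherwise state that Sidak covers six tests and use 0.0085.
4. Optionally, raise the resamples to 5000. Each tail of a 98.3% interval holds about 0.85%, or 8 to 9 of 1000 resamples. This is a refinement, not a correction of an error.

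Items 2 to 4 cost a few sentences of analysis text and a little computing. Item 1 is also only wording if controls already give a second score; if they do not, it means an added questionnaire. The downside is that indirect effects may be reported without a significant total effect, so the exploratory label must stay with them.
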